11.2. Study Discontinuation

Subjects who discontinue from treatment for any reason will be followed via telephone contact by the site for collection of data on survival including: cause(s) of death, disease progression, and posttreatment therapies for MPN-associated MF; until death, lost to follow up, or withdrawal of consent from the study.

Every attempt should be made to contact subjects during follow up unless subjects discontinue from the study. Every attempt should be made to collect all data on discontinued subjects.

The following events are considered sufficient reasons for discontinuing a subject from the study:

- Screen failure
 - The following information is to be captured in the subject's source documents and eCRF page(s): the date the informed consent forms (ICFs) were signed, demographics, prior ruxolitinib history, the reason a subject did not qualify for the

study, and the investigator's signature for the eCRF pages. Any adverse events experienced by a screen failure subject will be collected from the date of signing the ICF to the day the subject is confirmed as a screen failure. Serious adverse events occurring prior to treatment (after signing the ICF) are to be recorded within the eCRF, but do not require reporting to Celgene Drug Safety. Relevant information will also be recorded on the Screening Log.

- Withdrawal by subject
- Death
- Lost to follow-up
- Protocol deviation
- Study terminated by Sponsor
- Other (to be specified on the CRF)

The reason for study discontinuation should be recorded in the CRF and in the source documents.

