3.1.1. Study Periods

Screening Period

All enrolled subjects will undergo screening procedures during the screening period which must be completed within 28 days prior to the start of study treatment. This will serve to determine subject eligibility based on all inclusion and exclusion criteria defined in the protocol. For subjects that are receiving ruxolitinib during the screening period or that have potentially reversible laboratory abnormalities (or other criteria that excludes the subject from enrollment) detected during screening, the screening period may be extended to 35 days (additional 7 days).

If needed, enrollment will be preceded by a taper-off period for previous treatment according to the prescribing information and a washout period for previous treatment in line with the inclusion and exclusion criteria for the study which is to be started at least 14 days before enrollment. Specifically, ruxolitinib should be gradually tapered before the 14-day washout and supportive care provided to mitigate potential ruxolitinib withdrawal syndrome with close physician supervision. When screening a subject, it is necessary to account for the required duration of the ruxolitinib washout period of 14 days and the need to perform the MRI or CT scan within 5 days prior to enrollment.

Treatment Period

Upon confirmation of eligibility, subjects will be enrolled and receive treatment with fedratinib at a dose of 400 mg once daily orally continuously. Cycles are defined for administrative purposes as 4-week (28-day) periods. Unless otherwise noted, visit windows are \pm 3 days except for MRI/CT scan procedures which have a visit window of \pm 7 days.

For the first 3 cycles, site visits will be performed on Day 1 and Day 15 and thereafter on Day 1 for the subsequent cycles. At Cycle 1 Day 8 the site will contact the subject by telephone to assess occurrence and discuss management of nausea, vomiting and diarrhea.

Subjects may continue treatment with fedratinib until unacceptable toxicity, lack of therapeutic effect, progression of disease, or until consent is withdrawn.

[figure not shown]
All subjects will be monitored for adverse events during the study.

All subjects discontinued from protocol-prescribed therapy for any reason will be followed for at least a period of 30 days following the last dose of fedratinib.

Survival Follow-up Period

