6.3.2. Survival Follow-up

All subjects discontinued from protocol-prescribed therapy for any reason will be followed for survival, subsequent therapies, new malignancy and progression of myelofibrosis to acute myeloid leukemia (AML) every 3 months until death, up to 12 months after EOT, lost to follow-up, withdrawal of consent for further data collection, or study closure whichever comes first. See Section 10.7 for additional details on reporting.

A window of \pm 14 days is allowed for post treatment Survival Follow-up assessments; the visits should be performed every 3 months \pm 14 days and can be done by a documented telephone contact between site and subject.

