8.2. Prohibited Concomitant Medications

The following concomitant medications are specifically excluded during the course of the study:

- Cytotoxic, chemotherapeutic, targeted or investigational agents/therapies
- Immunomodulatory drug therapy (eg, thalidomide)
- Immunosuppressive therapy

- Systemic corticosteroids >10 mg/day prednisone or equivalent
- Hydroxyurea
- Interferon-alpha
- Anagrelide
- JAK inhibitors other than fedratinib
- Aspirin at doses of > 150 mg daily
- Any investigational agent

For information regarding clinically relevant P450 inducers, inhibitors, substrates, and Transporter Substrates refer to Section [8.3](#).

If a subject requires treatment with any new medications that are specifically excluded, the subject may need to be discontinued from treatment. The Investigator should consult the Medical Monitor regarding any questions about whether a new medication or dosage of existing medication would require the subject to discontinue from the study.

8.3. Clinically Relevant Cytochrome P450 Inducers, Inhibitors, Substrates, and Transporter Substrates

Fedratinib is metabolized by multiple cytochrome P450 enzymes (CYPs) in vitro, with prominent contribution from CYP3A4 and with a lesser contribution from CYP2C19.

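### Section 11.2 lets a subject who has not withdrawn consent be removed from the study for a protocol deviation, or an open-ended other reason, against the follow-up rules in the rest of the protocol

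*Combined protocol and SAP*

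**What the plan says.** The opening paragraph of Section 11.2 keeps everyone who stops treatment, whatever the reason, in telephone follow-up "until death, lost to follow up, or withdrawal of consent from the study". Two further instructions come next: "Every attempt should be made to contact subjects during follow up unless subjects discontinue from the study", and then "Every attempt should be made to collect all data on discontinued subjects".

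The section then lists reasons for leaving the study itself: "The following events are considered sufficient reasons for discontinuing a subject from the study". There are seven entries: screen failure, withdrawal by the subject, death, loss to follow-up, "Protocol deviation", termination by the sponsor, and an open entry to be specified on the CRF.

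Other places that bear on this:
- **Section 3.1.1:** subjects off therapy for any reason "will be followed for at least a period of 30 days following the last dose of fedratinib".
- **Section 6.3.2 (same rule in 3.1.1):** "All subjects discontinued from protocol-prescribed therapy for any reason will be followed for survival, subsequent therapies, new malignancy and progression of myelofibrosis" to AML, every 3 months. This ends at death, 12 months after end of treatment, loss to follow-up, withdrawal of consent for further data collection, or study closure.
- **Section 6.3.1:** all subjects have 30 days of adverse event follow-up after the last dose.
- **Table 3:** AML assessment runs from consent to death, loss to follow-up, withdrawal of consent or study closure.
- **Section 11.1:** protocol deviation is listed separately as a reason to stop fedratinib.
- **Section 8.2:** a subject who needs an excluded drug may have to come off treatment. The next sentence refers to the Medical Monitor any question about whether the drug "would require the subject to discontinue from the study".

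**The concern.** Stopping treatment and leaving the study are different events, and most of the protocol keeps them apart. The 11.2 list blurs them. A deviation is not a withdrawal of consent, and nothing about it prevents a site from telephoning the subject. Yet it is named as sufficient for leaving the study, with no type or severity of deviation specified, and leaving the study excuses further contact.

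Removal is decided after enrollment by people who know how the subject is doing. Some deviations, such as starting another myelofibrosis drug prohibited by Section 8.2, could plausibly go with a worse course. That is a judgment, since the documents give no data on it. If it is right, the missing follow-up would be informative. Because the wording permits removal without requiring it, two sites could also treat the same deviation differently.

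**Working it through.** **1. Match each 11.2 reason to the points at which follow-up may end (3.1.1, 6.3.2, Table 3, opening of 11.2).**
- Screen failure: never treated, so post-treatment follow-up does not arise.
- Withdrawal by the subject: corresponds to withdrawal of consent.
- Death: matches.
- Loss to follow-up: matches.
- Termination by the sponsor: corresponds to study closure.
- Protocol deviation: no counterpart anywhere.
- Other: no counterpart, and no limit on what it may cover.

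Five of the seven entries are consistent with the follow-up rules and two are not. The list is also not a plain copy of 11.1: it drops lack of efficacy, adverse event, progression and pregnancy, but keeps deviation.

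**2. What removal does to contact.** The clause on contact makes an exception for subjects who leave the study. The next sentence asks for all data on discontinued subjects without saying whether that means off treatment or off study. A site can read the pair either way.

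**3. What is still collected after removal.**
- Adverse events to day 30: required for all subjects by 6.3.1 and 10.1.
- All serious adverse events to day 30, and suspected-related ones made known at any later time: 10.5.
- Serious adverse events unresolved when participation ends: followed under 10.2.6.
- Later deaths, AML and new malignancies not suspected to be related: actively sought only through the 3-monthly contacts. AML and new malignancy are adverse events of special interest under 10.7.1.

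The main loss is therefore the survival follow-up. At one contact every 3 months for up to 12 months, that is 12 / 3 = 4 contacts per removed subject.

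**4. Durability endpoints.** Sections 9.6.4 and 9.6.5 count death as an event for durability of spleen response by imaging (DR) and by palpation (DRP), and otherwise censor at the last valid assessment. An unobserved death in a responder thus becomes a censoring. Two limits apply: only responders enter these analyses, and Table 2 sets the timeframe to the End of Treatment visit for DR and the 30-Day visit for DRP.

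**5. Sample size and power.** Inputs from Section 9.3: n = 100 evaluable, true rate 0.35, lower bound of the exact 95% interval to exceed 0.20. The lower bound for x responders is the 0.025 quantile of a Beta(x, n − x + 1) distribution. At n = 100 the smallest x with a bound above 0.20 is 29.
- P(X ≥ 29 | n = 100, p = 0.20) = 0.020.
- P(X ≥ 29 | n = 100, p = 0.35) = 0.915, which reproduces the stated figure of about 90%.

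For orientation, exact power is 94.7% at n = 110, 89.3% at n = 95 and 86.6% at n = 90. The 11.2 wording does not enter this calculation. A removed subject with a baseline and a post-baseline scan but no Cycle 6 scan stays in the denominator as a non-responder (9.6.1). Only removal before any post-baseline scan takes a subject out of the evaluable set, and the plan already allows about 10 such losses (110 − 10 = 100).

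**The case against.** The strongest reply is that 11.2 does not stop follow-up. Calling reasons sufficient permits removal without ordering it. The list includes death, screen failure and loss to follow-up, so it may serve only as disposition categories. The section still asks for all data on discontinued subjects, and its opening paragraph names no exit for a deviation. In 8.2 the sentence before the quoted phrase speaks of treatment, and the phrase itself belongs to an instruction to consult the Medical Monitor, which gives some central consistency for prohibited drugs.

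Much of this stands. A reader might infer that a deviation ends all safety, survival and AML follow-up, so that adverse events within 30 days go unobserved. The documents do not support that: 6.3.1, 10.1, 10.2.6 and 10.5 keep those obligations in place. Nor does 8.2 by itself remove anyone from the study.

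The conflict remains. The exception for contact is explicit, the request for data is ambiguous, and no other section recognises a deviation as the end of follow-up. Permissive wording makes uneven handling across sites more likely.

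**Conclusion.** The point holds as a contradiction in the text. Section 11.2 permits a subject who has not withdrawn consent to be removed for a protocol deviation, or an unspecified other reason, and excuses further contact, while 3.1.1, 6.3.1, 6.3.2, Table 3 and its own opening paragraph provide no such exit. The exposure is mainly later survival, AML and new-malignancy data. DR and DRP are touched only through responders whose deaths go unobserved, within the Table 2 timeframes. Sample size, power and the 30-day reporting duties are unaffected.

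The size cannot be estimated from the documents, because they do not say how many subjects would be removed. A reader might multiply out a death count: if 5 to 10% of 110 (about 6 to 11 subjects) were removed and 10 to 66% of them died in the following year, 6 × 0.10 = 0.6 to 11 × 0.66 = 7.3, or roughly 1 to 7 deaths. That should not be used. The removal rate and the lower mortality figure have no source. The 66% is 100 − 34 from Section 1.1.4, which describes patients at a median of 10 months after stopping ruxolitinib; it is not a 12-month risk, and this trial excludes life expectancy under 6 months. Nor would the count measure the effect on DR or DRP: at the planned 35% response rate, and if removal were unrelated to response, 6 to 11 subjects would include only about 2 to 4 responders (2.1 to 3.9).

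The conflict is worth correcting without any such number, because the correction is cheap.

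**What to change.** - Delete protocol deviation from the study-discontinuation list in 11.2. It remains in 11.1 as a reason for stopping fedratinib.
- State in 11.2 that a subject who deviates and has not withdrawn consent stays in the End of Treatment visit, the 30-Day visit and the survival and AML follow-up of 6.3.2.
- Limit the open other-reason entry so that it cannot recreate the same exit. Deleting deviation alone would leave the gap open.
- Reconcile the two consecutive sentences in 8.2, one of which refers to treatment and the other to the study. Which is intended is for the sponsor to settle.

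The cost is a few wording edits, a check that the CRF disposition reasons agree (the CRF is not among the documents), and a few more contacts that are already in the schedule.

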12. EMERGENCY PROCEDURES

12.1. Emergency Contact

In emergency situations, the Investigator should contact the responsible Clinical Research Physician/Medical Monitor or designee by telephone at the number(s) listed on the Emergency Contact Information page of the protocol (after title page).

In the unlikely event that the Clinical Research Physician/Medical Monitor or designee cannot be reached, please contact the global Emergency Call Center by telephone at the number listed on the Emergency Contact Information page of the protocol (after title page). This global Emergency Call Center is available 24 hours a day and 7 days a week. The representatives are responsible for obtaining your call-back information and contacting the on-call Celgene-Impact/contract research organization Medical Monitor, who will then contact you promptly.

Note: The back-up 24-hour global emergency contact call center should only be used if you are not able to reach the Clinical Research Physician(s) or Medical Monitor or designee for emergency calls.

12.2. Emergency Identification of Investigational Products

This is an open-label study; therefore, fedratinib will be identified on the package labeling.

13. REGULATORY CONSIDERATIONS

13.1. Good Clinical Practice

The procedures set out in this study protocol pertaining to the conduct, evaluation, and documentation of this study are designed to ensure that Celgene-Impact, its authorized representative, and Investigator abide by Good Clinical Practice (GCP), as described in International Council for Harmonisation (ICH) Guideline E6 and in accordance with the general ethical principles outlined in the Declaration of Helsinki. The study will receive approval from an IRB/EC prior to commencement. The Investigator will conduct all aspects of this study in accordance with applicable national, state, and local laws of the pertinent regulatory authorities.

13.2. Investigator Responsibilities

Investigator responsibilities are set out in the ICH Guideline for Good Clinical Practice and in the local regulations. Celgene-Impact staff or an authorized representative will evaluate and approve all Investigators who in turn will select their staff.

The Investigator should ensure that all persons assisting with the study are adequately informed about the protocol, amendments, study treatments, as well as study-related duties and functions, including obligations of confidentiality of Celgene-Impact information. The Investigator should maintain a list of Sub-investigators and other appropriately qualified persons to whom he or she has delegated significant study-related duties.

The Investigator is responsible for keeping a record of all subjects who sign an informed consent form (ICF) and are screened for entry into the study. Subjects who fail screening must have the reason(s) recorded in the subject's source documents.

The Investigator, or a designated member of the Investigator's staff, must be available during monitoring visits to review data, resolve queries and allow direct access to subject records (eg, medical records, office charts, hospital charts, and study-related charts) for source data verification. The Investigator must ensure timely and accurate completion of CRFs and queries.

The information contained in the protocol and amendments (with the exception of the information provided by Celgene-Impact on public registry websites) is considered Celgene-Impact confidential information. Only information that is previously disclosed by Celgene-Impact on a public registry website may be freely disclosed by the Investigator or its institution, or as outlined in the Clinical Trial Agreement. Celgene-Impact protocol, amendment and IB information is not to be made publicly available (for example on the Investigator's or their institution's website) without express written approval from Celgene-Impact. Information proposed for posting on the Investigator's or their institution's website must be submitted to Celgene-Impact for review and approval, providing at least 5 business days for review.

At the time results of this study are made available to the public, Celgene-Impact will provide Investigators with a summary of the results that is written for the lay person. The Investigator is responsible for sharing these results with the subject and/or their caregiver as agreed by the subject.

13.3. Subject Information and Informed Consent

The Investigator must obtain informed consent of a subject and/or a subject's legal representative prior to any study related procedures.

Documentation that informed consent occurred prior to the study subject's entry into the study and of the informed consent process should be recorded in the study subject's source documents including the date. The original ICF signed and dated by the study subject and by the person consenting the study subject prior to the study subject's entry into the study, must be maintained in the Investigator's study files and a copy given to the study subject. In addition, if a protocol is amended and it impacts on the content of the informed consent, the ICF must be revised. Study subjects participating in the study when the amended protocol is implemented must be re-consented with the revised version of the ICF. The revised ICF signed and dated by the study subject and by the person consenting the study subject must be maintained in the Investigator's study files and a copy given to the study subject.

13.4. Confidentiality

Celgene-Impact affirms the subject's right to protection against invasion of privacy and to be in compliance with ICH and other local regulations (whichever is most stringent). Celgene-Impact requires the Investigator to permit Celgene-Impact's representatives and, when necessary, representatives from regulatory authorities, to review and/or copy any medical records relevant to the study in accordance with local laws.

Should direct access to medical records require a waiver or authorization separate from the subject's signed ICF, it is the responsibility of the Investigator to obtain such permission in writing from the appropriate individual.

13.5. Protocol Amendments

Any amendment to this protocol must be approved by the Celgene-Impact Clinical Research Physician/Medical Monitor. Amendments will be submitted to the IRB/EC for written approval. Written approval must be obtained before implementation of the amended version occurs. The written signed approval from the IRB/EC should specifically reference the Investigator name, protocol number, study title and amendment number(s) that is applicable. Amendments that are administrative in nature do not require IRB/IEC approval but will be submitted to the IRB/IEC for information purposes.

13.6. Institutional Review Board/Independent Ethics Committee Review and Approval

Before the start of the study, the study protocol, ICF, and any other appropriate documents will be submitted to the IRB/EC with a cover letter or a form listing the documents submitted, their dates of issue, and the site (or region or area of jurisdiction, as applicable) for which approval is sought. If applicable, the documents will also be submitted to the authorities in accordance with local legal requirements.

Fedratinib can only be supplied to an Investigator by Celgene-Impact or its authorized representative after documentation on all ethical and legal requirements for starting the study has

been received by Celgene-Impact or its authorized representative. This documentation must also include a list of the members of the IRB/EC and their occupation and qualifications. If the IRB/EC will not disclose the names, occupations and qualifications of the committee members, it should be asked to issue a statement confirming that the composition of the committee is in accordance with GCP. For example, the IRB General Assurance Number may be accepted as a substitute for this list. Formal approval by the IRB/EC should mention the protocol title, number, amendment number (if applicable), study site (or region or area of jurisdiction, as applicable), and any other documents reviewed. It must mention the date on which the decision was made and must be officially signed by a committee member. Before the first subject is enrolled in the study, all ethical and legal requirements must be met.

The IRB/EC and, if applicable, the authorities, must be informed of all subsequent protocol amendments in accordance with local legal requirements. Amendments must be evaluated to determine whether formal approval must be sought and whether the ICF should also be revised.

The Investigator must keep a record of all communication with the IRB/EC and, if applicable, between a Coordinating Investigator and the IRB/EC. This statement also applies to any communication between the Investigator (or Coordinating Investigator, if applicable) and regulatory authorities.

Any advertisements used to recruit subjects for the study must be reviewed by Celgene-Impact and the IRB/EC prior to use.

